The UW Institute for Clinical and Translational Research (ICTR) Study Monitoring Service (SMS) program, a robust academic equivalent to the industry Contract Research Organization (CRO) standards for ongoing study monitoring, will be contracted for the proposed study. The ICTR Study Monitoring Service staff will work very closely with the Medical College of Wisconsin (MCW) Study Monitoring Service staff to conduct monitoring visits throughout the life cycle of the study (e.g., Site Initiation Visit, Interim Monitoring Visits, and Close-Out Visit). Study monitoring visits will occur off-site (remotely) and/or on-site at a frequency necessitated by the protocol risk and complexity.

For this study, the UW ICTR SMS will conduct a Site Initiation Visit (SIV) at each study site, coordinating efforts with MCW SMS staff at their study site. The SIV will be conducted with the site research personnel in person after IRB approval is obtained and prior to subject enrollment. The SIV will include a detailed review of the protocol, Good Clinical Practice guidelines, and data management expectations of the research team at the study site and the SMS personnel.

Following the Site Initiation Visit (SIV), SMS personnel will conduct ongoing Interim Monitoring Visits (IMVs) for all data collection sites, either on-site, remotely or a combination of both, following enrollment of the first subject(s) and throughout the duration of the study. During IMVs, the monitors will review study materials, including but not limited to: regulatory files, consent forms, case report forms, and device accountability logs.

For this study, UW ICTR and MCW SMS personnel plan to review study-related subject records for 10-20% of the enrolled subjects. Monitoring could consist of full or partial review of study records, depending on risk level and observed compliance. The first subjects enrolled will be monitored in their entirety, with the additional number to be randomly selected from each of the study sites. SMS personnel could increase the percentage of study or subject records to be reviewed if warranted.

Within ICTR OnCore, ICTR SMS personnel will verify the accuracy of and validate entered data by comparing the data entered with the information provided on the source document. All modifications made to the data are tracked and logged from the point of initial entry until the data is locked. The study monitor(s) will work closely with the MARCH DSMB statistician and the study statistician to conduct

periodic central data reviews, with follow-up conducted by the study monitors for any data discrepancies identified.

UW ICTR SMS personnel will conduct a Close-Out Visit (COV) upon completion of the study at the study site, working closely with MCW SMS personnel at the MCW study site.

STUDY TIMELINE

This project will occur over three years, with the clinical trial occurring in the first two years and statistical analysis and manuscript preparation in year three. Each site will recruit ~167 participants. Prior to initiation of the study, we will finalize the protocol, obtain IRB approval, and hold a start-up meeting to train the study staff.

REFERENCES

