In our pilot study of 91 community-dwelling postmenopausal women of European ancestry treated with 2300-2500 IU of vitamin D₃ daily for 4-6 months, we utilized novel liquid chromatography, tandem mass spectroscopy (LC-MS/MS) methodology to evaluate serum levels of cholecalciferol (vitamin D₃) and 24,25(OH)₂D at baseline and after 4-6 months. We observed the anticipated relationship with cholecalciferol: a greater increase in circulating vitamin D₃ is associated with a greater increment in 25(OH)D. Additionally, we reproduced the observation of others [Wagner et al., 2011] that a higher ratio of 24,25(OH)₂D/25(OH)D after supplementation is associated with a less robust increase in 25(OH)D. Thus, our pilot work supports the premise that smaller increments in 25(OH)D may result from relatively low vitamin D₃ input (presumably from poor absorption) and/or greater degradation. To this end, we performed multiple regression analysis to determine the characteristics that might enable prediction of the 25(OH)D achieved with supplementation. The equation from the final model was: post-treatment 25(OH)D = 8.3 + (1.05*baseline 25(OH)D) – (7.7*baseline 24,25(OH)₂D) + (0.53*follow-up cholecalciferol) + (4.2*follow-up 24,25(OH)₂D). This model had an adjusted $R^2 = 0.55$ with $p < 0.001$ for all the parameters, thus accounting for approximately half of the variance in the final 25(OH)D level. The baseline values of cholecalciferol could not be used in this model because the data were highly skewed (virtually all values were zero since the assay is currently not capable of measuring very low concentrations of cholecalciferol). Nonetheless, these preliminary data support the dosing algorithm described below.

HYPOTHESES AND SPECIFIC AIMS

Aim 1:

Determine the efficacy of our dosing algorithm in achieving total 25(OH)D concentrations of 35-50 ng/mL in women of European and African ancestry.

To validate our vitamin D₃ dosing algorithm, we will conduct a randomized, double-blind, controlled, six-month duration clinical trial of daily oral vitamin D₃ to determine the efficacy of dosing following our algorithm compared to 2500 IU/day (control arm) in achieving the target total 25(OH)D concentration of 35-50 ng/mL. Participants will be community-dwelling post-menopausal women of European and African ancestry, who have a baseline total serum 25(OH)D of ≥ 10 but < 30 ng/mL.

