H1a: The percent of individuals with total 25(OH)D of 35-50 ng/mL will be significantly higher in the dosing algorithm arm than in the control arm.

H1b (exploratory aim): The percent of African ancestry women with total 25(OH)D of 35-50 ng/mL will be similar to (i.e., not significantly different than) that in women of European ancestry.

Aim 2:

Determine additional factors that predict response to vitamin D supplementation.

We will expand our predictive model to include baseline serum cholecalciferol and body composition, measured by dual-energy x-ray absorptiometry (DXA), and genotypes in the *GC* and *CYP2R1* genes. In exploratory analyses we will also determine the effect of self-reported ancestry on our dosing algorithm.

H2a: Baseline body mass, but not total body fat, will be negatively associated with total 25(OH)D after supplementation, indicating that individuals with larger body size, not just body fat, will require a higher dose of vitamin D₃ to attain the target total 25(OH)D range.

H2b: Baseline cholecalciferol will be positively associated with 25(OH)D after supplementation, where individuals with higher values will require a lower dose.

H2c: There will be a negative association between the number of risk alleles in the two genes and total 25(OH)D after supplementation, where individuals with more risk alleles will require a higher dose.

Completion of these aims will allow us to validate and refine our vitamin D dosing algorithm. This predictive tool will allow clinical estimation of the dose needed to achieve a target 25(OH)D level, advancing clinical care by allowing personalization of vitamin D supplementation. Moreover, the insight gained from the proposed study will enable clinical trials of other vitamin D-related outcomes to achieve more effective vitamin D supplementation by using our dosing algorithm. This will enhance future research proposals by radically improving the study design.

STUDY DESIGN

Study Design and Population.

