The proposed study is a randomized, double-blind, controlled, multi-center clinical trial of six months of daily oral vitamin D₃ (cholecalciferol). This study will randomize 334 community-dwelling post-menopausal women of European and African ancestry (~167 from each ancestry) in a 1:1 ratio between the control arm and the dosing algorithm arm using stratified block randomization with a block size of six and stratification by site (ancestry). The sample size of 334 includes 10% over-recruitment to allow for loss to follow-up. The proposed study will focus on post-menopausal women because this is the subset of the population that both [name] and [name] preliminary data are drawn from. Moreover, 25(OH)D concentrations are typically lower in women and in older individuals, since production of vitamin D in the skin following sun exposure decreases with age. Therefore, this group of individuals is likely to benefit the most from vitamin D supplementation, especially when personalized based on biology using our dosing algorithm.

Vitamin D Preparation and Dosing.

All vitamin D₃ preparations will be produced by Tishcon Corp (Westbury, NY). Vitamin D₃ content of these preparations will be independently validated in the laboratory of [name] prior to study initiation and annually thereafter to assure stability. The control group will receive 2500 IU of vitamin D₃ daily while the dosing algorithm group will initially receive 1000, 2500, or 4000 IU daily. The rationale for these dosing arms is based on our pilot data. First, we aim to reduce the variation in achieved 25(OH)D following vitamin D supplementation, bringing more individuals into the target range of 35-50 ng/mL. In our pilot study, participants received 2300-2500 IU/day, a dose similar to many other vitamin D supplementation trials. Therefore, to test the alternate hypothesis that our dosing algorithm will improve vitamin D supplementation beyond that typically given in clinical trials, the appropriate control group should receive 2500 IU/day. Second, in our multiple regression analysis to determine characteristics that predict 25(OH)D achieved after supplementation, the following equation had an adjusted R^2 of 0.55 ($p < 0.001$): post-treatment 25(OH)D = 8.3 + (1.05*baseline 25(OH)D) –

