In the primary analyses for Aim 1 (H1a), treatment group (control versus dosing algorithm) will be the independent variable; for H1b, ancestral group (European versus African ancestry) will be the independent variable and only individuals in the dosing algorithm group will be included. For both H1a and H1b, the dependent variable will be the percent of individuals with a 25(OH)D concentration of 35-50 ng/mL at the three- and six-month follow-up visits. A two-sample test for binomial proportions will be used. We will also determine the effect of treatment group and ancestry on free (bioavailable) 25(OH)D concentration using an analysis of variance.

The control group will be used as an unbiased external validation of our dosing algorithm, in which we will repeat the multiple regression analysis in the control sample and compare the coefficients to those in our original equation. In Aim 2 (H2a-c), we will further develop our dosing algorithm by determining if baseline serum cholecalciferol, baseline body composition, and genotypes in the *GC* and *CYP2R1* genes are associated with response to vitamin D₃ supplementation. In exploratory analyses we will include two-way interaction terms between ancestry and each of our primary predictors to determine if the effect of any of these biologic predictors varies by ancestral group.

Sample Size Justification.

For H1a, the outcome variable will be the percent of individuals with a 25(OH)D concentration of 35-50 ng/mL at the three- and six-month visits. Based on our preliminary data, we expect 40% of the individuals receiving 2500 IU/day to achieve 25(OH)D of 35-50 ng/mL. We expect our dosing algorithm to increase this to at least 55%, a conservative estimate. We calculated the sample size required in each arm to detect this difference with power of 80% and a one-sided significance level (α) of 0.05. A sample of 167 participants in each arm, decremented to 150 by a 10% loss to follow-up will be required.

In the multiple regression models for H2a-c, with a total sample size of 150 from the control arm, an α of 0.05, and power of 80% we would be able to detect a factor that accounts for as little as 8% of the variation in 25(OH)D concentration after vitamin D supplementation.

Multisite Conduct Plan

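### H1b (exploratory) defines similarity between ancestries as a non-significant difference, with no margin, in about 75 women per ancestry

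*Combined protocol and SAP*

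**What the plan says.** Aim 1 (Hypotheses and Specific Aims) labels H1b exploratory and predicts that the percentage of African ancestry women in the target range "will be similar to (i.e., not significantly different than) that in women of European ancestry". The words after the i.e. serve as the definition of similar.

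Statistical Methods makes ancestry the independent variable for H1b and says that "only individuals in the dosing algorithm group will be included". The outcome is the percentage in range at the three- and six-month visits. For both H1a and H1b, "A two-sample test for binomial proportions will be used".

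No margin, confidence-interval rule, alpha, sidedness or power is given for H1b. The Sample Size Justification covers H1a, "with power of 80% and a one-sided significance level" of 0.05, and H2a-c. It does not mention H1b. The plan also does not say whether the two visits are tested separately.

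**The concern.** A test of difference can show that two proportions differ. When it fails to do so, the reason may be that they are close or that the sample is small, and the p-value cannot tell these apart. Making non-significance the definition of similarity rewards imprecision: the more women are lost, the more likely the hypothesis is to be confirmed.

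This matters because the equation behind the algorithm comes from "In our pilot study of 91 community-dwelling postmenopausal women of European ancestry", while the trial's stated goal is to validate the algorithm in both ancestries. H1b is the only comparison of target attainment between ancestries that the plan describes. The ancestry-by-predictor interactions and the free 25(OH)D analysis address other quantities. A statement that attainment was similar could support use of the algorithm in the group in which it was not developed, when the data are compatible with a sizeable shortfall.

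**Working it through.** **Inputs**
- 334 women randomized 1:1, about "167 from each ancestry" (Study Design and Population).
- 10% loss to follow-up; planning rates 40% (control) and 55% (algorithm); one-sided alpha 0.05; 80% power (Sample Size Justification, for H1a).
- Assumed here: 55% attainment in one ancestry group. This is the H1a planning rate for the algorithm arm.

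**The plan's own figure.** For 40% versus 55%, one-sided 0.05 and 80% power, the normal-approximation formula gives 136 per arm, and 150 with continuity correction. Then 150/0.9 = 167. The H1a sample size reproduces and is not in question.

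**Size of the H1b comparison.** 334/4 = 83.5 randomized per ancestry in the algorithm arm; 83.5 × 0.9 = 75.15, so about 75 evaluable.

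**Precision.** The 95% CI half-width is 1.96 × √(2 × 0.55 × 0.45/75) = 0.159, about 16 points either way.

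**Chance that a true gap d is non-significant.** Approximately 1 − Φ[(d − z·SE₀)/SE₁], with SE₀ = √(2p̄(1−p̄)/n) and SE₁ = √((p₁(1−p₁) + p₂(1−p₂))/n).

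For 55% versus 40%, n = 75, two-sided 0.05:
- p̄ = 0.475, SE₀ = 0.0815, SE₁ = 0.0806
- (0.15 − 1.96 × 0.0815)/0.0806 = −0.12
- power 45%, so non-significant 55% of the time

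| True gap | Two-sided 0.05, n = 75 | One-sided 0.05 toward the gap, n = 75 | Two-sided 0.05, n = 83 (no loss) |
|---|---|---|---|
| 10 points | 77% | 66% | 75% |
| 15 points | 55% | 42% | 51% |
| 20 points | 30% | 20% | 26% |
| 25 points | 12% | 7% | 9% |

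Exact binomial enumeration of the two-sided test at n = 75 gives 75.6%, 52.9%, 28.5% and 11.0%. A similar call is a coin flip at a true gap of 16.0 points (two-sided) or 13.4 points (one-sided). The gap detectable with 80% power is 22.5 or 20.1 points respectively.

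**Both visits.** If non-significance were required at both visits (two-sided, the same gap at each, between-visit correlation assumed 0.3 to 0.9), the chances are 62–72% at 10 points, 35–48% at 15 and 13–24% at 20.

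**Dependence on sample size.** At a true 15-point gap, two-sided, the rule returns similar 26% of the time with 150 per group, 55% with 75 and 73% with 40.

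**A single result.** With 41/75 (54.7%) against 30/75 (40.0%), the difference is 14.7 points, p = 0.07, and the 95% CI runs from −1.1 to +30.5 points. The two-sided rule calls this similar.

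**What a proper equivalence test could do.** Two one-sided tests at 0.05 each, true difference zero, 55% in both groups, n = 75; power is 2Φ(margin/SE − 1.645) − 1 with SE = 0.0812, set to zero if negative. The documents give no margin, so a range is shown.

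| Margin | Power at n = 75 | n per ancestry for 80% power |
|---|---|---|
| 10 points | 0% | 424 |
| 15 points | 16% | 189 |
| 20 points | 59% | 106 |
| 25 points | 85% | 68 |

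**The case against.** H1b is labelled exploratory. The trial claims no power for it, and neither the sample size nor the H1a conclusion depends on it. The plan states a hypothesis and names a test; it nowhere says in so many words that p > 0.05 will be reported as similarity. A sensible report would give both proportions with an interval, and nothing forbids that. Aim 2 also plans exploratory work on self-reported ancestry, so the ancestry question does not rest on H1b alone. The intent-to-treat statement in Statistical Methods points to about 83 women per ancestry, not 75. The both-visits and one-sided calculations rest on rules the plan does not state for H1b, and the unclear handling of visits affects H1a equally.

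Much of this stands as a limit on the consequences. The exploratory label lowers the weight of the conclusion, and H1a is untouched. It does not remove the defect: the plan itself equates similar with not significantly different, and the other ancestry analyses do not compare target attainment. Using 83 women moves the two-sided 15-point figure only from 55% to 51%. The one-sided and both-visits figures are sensitivity checks; the conclusion does not depend on them.

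**Conclusion.** The concern holds. As written, H1b would let a moderate real gap of about 10 to 15 points be reported as similarity more often than not under a two-sided 0.05 test (77% and 55%). Gaps of 25 points or more would usually be detected.

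The figures assume 55% attainment in one group, an even ancestry split and about 75 evaluable women per ancestry. The split is only a target, and the Amendment 5 summary notes that each site may now enroll both ancestries; an uneven split would reduce power further. The logical fault does not depend on any of these assumptions. It is confined to the interpretation of an exploratory comparison, but it should be corrected because it concerns the population in which the algorithm is least tested.

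**What to change.** In H1b, delete the parenthetical that defines similar as not significantly different. In Statistical Methods, replace the H1b test with wording such as:

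> In the dosing algorithm arm, the African-minus-European difference in the proportion with total 25(OH)D of 35-50 ng/mL will be reported at each follow-up visit with its 95% CI, as an exploratory estimate. A non-significant difference will not be interpreted as similarity.

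If a formal similarity claim is wanted, the sponsor must state and justify a margin before the ancestry comparison is seen. At this sample size a 10-point margin could not be met, and a 15-point margin would probably be inconclusive (power 16% with 75 per ancestry, 23% with 83).

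The cost is an edit to two sections, with no new participants or data and no change to H1a. The downside is a less favourable H1b conclusion: an estimate of the ancestry difference, good to about ±16 points, in place of a claim of similarity.

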$(7.7 \times \text{baseline } 24,25(\text{OH})_2\text{D}) + (0.53 \times \text{follow-up cholecalciferol}) + (4.2 \times \text{follow-up } 24,25(\text{OH})_2\text{D})$. Using only the baseline values, which would be available at an initial clinical visit, including baseline cholecalciferol, $\text{post-treatment } 25(\text{OH})\text{D} = 18.19385 + (0.65967 \times \text{baseline } 25(\text{OH})\text{D}) + (1.02393 \times \text{baseline } 24,25(\text{OH})_2\text{D}) + (0.13564 \times \text{baseline cholecalciferol})$. For the current study, the dosing at both baseline and the 3-month follow-up visit will be determined using this equation to predict post-treatment 25(OH)D (at the 3-month follow-up visit, the 3-month values will be substituted for the baseline values in the equation). Specifically, for those whose predicted 25(OH)D is ≥ 35 ng/mL and < 50 ng/mL, we will administer a dose of 2500 IU daily. For those whose predicted 25(OH)D is < 35 ng/mL, we will administer 4000 IU/day and for those whose predicted 25(OH)D is > 50 ng/mL we will administer 1000 IU/day. The target 25(OH)D range was selected as nearly all experts agree that 25(OH)D levels above ~ 30 - 32 ng/mL are adequate; hence we have chosen a target level ≥ 35 ng/mL to account for assay variability, thereby assuring that all have concentrations > 30 - 32 ng/mL. An upper limit of 50 ng/mL was selected based on evidence suggesting that 25(OH)D levels above this value might have adverse effects [Sempos et al., 2013; Stolzenberg-Solomon et al., 2010]. All three of the daily doses are within the range considered to be safe by a recent Institute of Medicine report [Ross 2011].

INCLUSION/EXCLUSION CRITERIA

Inclusion criteria:

- Healthy, community-dwelling postmenopausal woman (natural menopause, 12 consecutive months without menstruation, or surgical menopause and \geq age 55, or surgical menopause and postmenopausal symptoms \geq 12 months ago)
- Self-reported $> 50\%$ European or $> 50\%$ African ancestry
- Able and willing to sign informed consent as affirmed by research staff person obtaining consent
- Screening serum 25(OH)D concentration of 10.0-29.9 ng/mL
- Willing to not alter the amount of their baseline vitamin D supplementation during the course of this study
- Willing to use sunscreen (SPF ≥ 15) when sun exposure of > 15 minutes is expected during the months of May through September

Exclusion criteria:

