Adverse event recording		X	X	X
Assess compliance			X	X

VITAMIN D PREPARATION

Capsules containing 1000, 2500, and 4000 IU of vitamin D₃ will be obtained from Tischo corporation (Westbury, NY). The capsules will be protected from light and not stored above 25° C. Participants will be instructed to take their vitamin D₃ capsules with supper daily. Compliance with study supplementation will be documented by capsule count at the time of each study visits.

VITAMIN D ACCOUNTABILITY

Subjects will be mailed 110 capsules following the Baseline visit. The subjects will be asked to bring any unused supplement to the 3-month visit to be counted and re-dispensed. An additional 110 capsules will be mailed to the subjects following the receipt of their 3-month vitamin D panel lab values. All unused supplement will be returned at their 6-month visit to be counted and retained by the study team.

BLOOD COLLECTION, LABORATORY ANALYSES, AND BODY COMPOSITION

Blood collection.

Blood will be collected via venipuncture into vacutainer tubes. For subjects who agree to optional banking, serum aliquots will be obtained and banked for future study of markers relevant to vitamin D assessment. Banked samples will be stored in a locked -80 freezer. Stored samples will be labeled with subject ID number, initials and collection date.

All blood specimens will be stored and managed at the University of Wisconsin. Calcium, vitamin D and PTH tests will be conducted at the UW Health Clinical Research Laboratory, WNPRC or [name] research lab. The whole blood for DNA extraction will be frozen at -80°C on the day of collection until transportation in batches to the University of Wisconsin DNA Sequencing Facility for DNA extraction and genotyping

Vitamin D Panel.

We will obtain serum concentrations of vitamin D₃ (cholecalciferol; an indicator of vitamin D₃ absorption), 25-hydroxyvitamin D₃ [25(OH)D₃], 25-hydroxyvitamin D₂ [25(OH)D₂], the C3-epimer of 25(OH)D₃ [3-epi-25(OH)D₃] (a potentially inactive or less active metabolite), and 24,25-dihydroxyvitamin D [24,25(OH)₂D] (an indicator of 25(OH)D degradation). The vitamin D panel will be run in the UW WIMR laboratory by liquid chromatography tandem mass spectrometry (LC-MS/MS).

Additional Laboratory Analyses.

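### The month-3 dosing step puts on-treatment values into a baseline equation, so women on 4000 IU who measure about 25.5 to 34.9 ng/mL, below target, are stepped down to 2500 IU

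*Combined protocol and SAP*

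**What the plan says.** Vitamin D Preparation and Dosing (under Study Design) gives a dosing equation, introduced with "Using only the baseline values, which would be available at an initial clinical visit":

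predicted 25(OH)D = 18.19385 + 0.65967 × 25(OH)D + 1.02393 × 24,25(OH)2D + 0.13564 × cholecalciferol.

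It is applied at baseline and again at month 3, where "at the 3-month follow-up visit, the 3-month values will be substituted for the baseline values in the equation". The dose bands are the same at both visits: "for those whose predicted 25(OH)D is ≥ 35 ng/mL and < 50 ng/mL, we will administer a dose of 2500 IU daily", with 4000 IU for predictions below 35 and 1000 IU for predictions above 50. No other section gives a separate month-3 rule, an adjustment for current dose, or an override based on the measured level.

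The same section supports the target by saying that "nearly all experts agree that 25(OH)D levels above ~ 30 - 32 ng/mL are adequate", and sets the lower limit at 35 to leave room for assay variability. Vitamin D Accountability says "An additional 110 capsules will be mailed to the subjects following the receipt of their 3-month vitamin D panel lab values", so the measured value is known before the new capsules go out. Statistical Methods and Sample Size Justification define the H1a outcome as 25(OH)D of 35-50 ng/mL at both the three- and six-month visits, with a single assumed contrast of 40% against 55%.

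**The concern.** The equation is built to predict, from pre-treatment values, where a woman will end up. At month 3 it receives values already raised by up to three months of 1000, 2500 or 4000 IU and treats them as a starting point. A woman who has responded but is still short of 35 then looks like someone who will do well on 2500 IU, and her dose falls.

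Month 6 is part of the H1a outcome, and H1b uses the algorithm arm alone. If the arm falls short at month 6, the result will not show whether the baseline equation or the month-3 step was responsible, although Aim 1 is meant to validate the equation. The sample-size section assumes one contrast for both visits and makes no allowance for the dose change between them.

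**Working it through.** **Inputs.** Coefficients, dose bands and the eligible range (screening 25(OH)D 10.0-29.9 ng/mL) come from the dosing and inclusion sections. Month-3 metabolite levels are not given, and the equation states no units for them. The values used below are assumptions, taken as ng/mL.

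**The plan's own figure.** No switching point is stated for month 3. The sample size does reproduce: 40% against 55%, one-sided 0.05, 80% power, with continuity correction gives 150 per arm, and 150 / 0.90 = 166.7, rounded up to 167. The problem below is not in that arithmetic.

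**Step 1: cut-offs with both metabolites at zero.**
- Prediction of 35: (35 − 18.19385) / 0.65967 = 25.48 ng/mL.
- Prediction of 50: (50 − 18.19385) / 0.65967 = 48.22 ng/mL.

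**Step 2: what the rule does at month 3 (metabolites at zero).**

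| Measured 25(OH)D | Prediction | Dose assigned |
|---|---|---|
| 25.5 | 35.02 | 2500 IU |
| 28 | 18.19385 + 0.65967 × 28 = 36.66 | 2500 IU |
| 30 | 37.98 | 2500 IU |
| 34.9 | 41.22 | 2500 IU |

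A woman with a baseline of 20 has a prediction of 31.39 and starts on 4000 IU. If she reaches 30 at month 3, she is below target and is cut to 2500 IU. At 28 she would be cut although she is below even the 30-32 that the protocol calls adequate.

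**Step 3: effect of positive metabolite values.** Both coefficients are positive, so real values can only move the cut-offs down. Each unit of 24,25(OH)2D lowers them by 1.02393 / 0.65967 = 1.55 ng/mL, and each unit of cholecalciferol by 0.13564 / 0.65967 = 0.21.

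| Assumed 24,25(OH)2D | Assumed cholecalciferol | 2500 IU from | 1000 IU above |
|---|---|---|---|
| 0 | 0 | 25.48 | 48.22 |
| 2 | 0 | 22.37 | 45.11 |
| 4 | 0 | 19.27 | 42.01 |
| 0 | 10 | 23.42 | 46.16 |

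At a measured 34.9, the two metabolite terms together would have to exceed 50 − 41.22 = 8.78 before she was cut to 1000 IU instead.

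**Step 4: no way up.** A woman on 2500 IU had a baseline prediction of at least 35. If none of her three values has fallen, her month-3 prediction is at least as high. She can stay or go down, but she cannot go to 4000 IU, even if she still measures below 35.

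**Step 5: implied further rise.** With metabolites at zero, the prediction exceeds the current value whenever 25(OH)D is below 18.19385 / (1 − 0.65967) = 53.46. The excess is 9.52 at 25.5 and 6.32 at 34.9. If the equation came from the pilot, whose women were "treated with 2300-2500 IU of vitamin D₃ daily for 4-6 months", that excess is the gain from starting such a dose, counted a second time. The pilot origin is an inference: the Background reports that for baseline cholecalciferol "virtually all values were zero since the assay is currently not capable of measuring very low concentrations of cholecalciferol" and leaves it out of the pilot model, yet the dosing equation includes it. Steps 1 to 4 do not depend on this.

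**Step 6: what cannot be computed.** The documents give no month-3 distribution on 4000 IU, no dose-response and no kinetics. As an assumption only, if each 1000 IU is worth 2 to 6 ng/mL at plateau, a cut of 1500 IU lowers a woman's eventual level by 1.5 × 2 = 3 to 1.5 × 6 = 9 ng/mL compared with staying on 4000 IU. How many women this takes out of range, or keeps from exceeding 50, is unknown.

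**The case against.** Re-dosing at month 3 is a prespecified part of the intervention. H1a compares that whole strategy with fixed 2500 IU, so randomisation protects the comparison and the type I error is unaffected. The month-3 outcome is measured before the step takes effect. 25(OH)D may still be rising at month 3, so some women in the 25.5-34.9 band may reach 35 on the lower dose. The protocol also has a stated reason to avoid levels above 50.

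All of this stands as far as validity goes. It does not justify the step-down. A level that is still rising is a reason to keep the dose, and the ceiling of 50 is no reason to cut a woman measured below 35. No section argues for lowering the dose of under-target women.

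A reader might go further and infer that the rule puts the algorithm arm behind control at month 6. The documents do not support that. Women below the lower cut-off are still assigned 4000 IU, and those cut from 4000 to 2500 IU then take the control dose after three months on more. Against control, a loss would have to come mainly from women stepped down to 1000 IU, and their number is unknown. A reader might also take the equation's pilot origin as established, which it is not.

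**Conclusion.** The concern holds as a defect in the written month-3 rule and should be fixed. The cut-offs of 25.48 and 48.22 ng/mL, and the absence of any upward move for a woman whose values have not fallen, follow from the printed coefficients. Setting the metabolites to zero gives the highest cut-offs, so the true lower one is at or below 25.5. The rule conflicts with the stated aim of getting a larger share of women into 35-50 and may lower the algorithm arm's month-6 rate. The size of that effect, and whether the arm still beats control, cannot be determined from the documents. The randomised comparison of the full strategy is valid, and month 3 gives a clean reading of the baseline equation.

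**What to change.** Add one sentence to the dosing section: at month 3, the dose is not lowered for any woman whose measured 25(OH)D is below 35 ng/mL; she keeps her current dose. Leave the rest of the rule as written, and describe the month-6 result as the equation plus this guard. The guard is deliberately narrow. It does not move anyone up, and it leaves the step-down from about 48.2 in place. Holding every dose until the measured level passes 50 would let more women exceed the protocol's own ceiling.

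If the rule is not amended:
- put the pilot's 4-6-month values through the equation and count the under-target women who would be given 2500 IU or less (those women took 2300-2500 IU, so this is only a guide to the 4000 IU group);
- state expected in-range rates for months 3 and 6 separately;
- base the conclusion about the baseline equation on month 3.

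The cost is an amendment and IRB approval. No new visits, panels, capsule strengths or mailings are needed. A few more women may exceed 50 ng/mL. The document is already at Amendment 5, so some women may have passed month 3, and month 6 would then be reported by rule version. If half of the 150 per arm fell under each version (assumed), the 95% half-width for 40% against 55% would go from 1.96 × √(0.4875/150) = 11.2 points to 1.96 × √(0.4875/75) = 15.8, where 0.4875 = 0.40 × 0.60 + 0.55 × 0.45. One-sided power without continuity correction would go from 83% to 58%. The month-3 comparison keeps everyone.
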